7.2.6 Physical examination and health history

The physical examination will include an assessment of the following: general appearance, skin, head and neck (including eyes, ears, and throat), lymph nodes, thyroid, musculoskeletal/extremities (including spine), cardiovascular, lungs, abdomen, and neurological systems. Health history assessment will include personal and family health history. All physical exam and health history documentation will be directly captured using REDCap. For participants who have lapses in study participation at Visit 1, the physical exam and health history may be considered relevant for up to 8 weeks after they were conducted. A pre-existing physical examination and health history may be used to determine eligibility if it was obtained within 3 weeks prior to the date of consent.

7.2.7 Laboratory assessments

Blood samples for determination of clinical chemistry and hematology parameters will be taken at the time of the baseline visit and at the final visit (Table 2). For participants who have lapses in study participation at Visit 1, medical lab assessments may be considered relevant for up to 8 weeks from collection (up to 11 weeks if it was obtained 3 weeks prior to the date of consent.). Pre-existing labwork may be used to determine eligibility if it was obtained within 3 weeks prior to the date of consent. Source data will be the lab reports, and the data will be entered into REDCap. Date and time of collection and results will be recorded. Collecting bloodwork for genetics will be optional on the part of the participant. The use of the genetic materials will be exploratory and used in relation to imaging and treatment findings. All blood collected for genetics analysis will be stored at Yale University, the site of the Principal Investigator. Any extracted genetic data will then be made available through the National Institutes of Health database of Genotypes and Phenotypes (daGaP). The following laboratory variables will be measured:

Hematology	Infectious Disease	Clinical Chemistry	Urine
Complete Blood Count (CBC) with Differential	Hepatitis B panel (Hep B surface antigen, surface antibody and core antibody)	Comprehensive Metabolic Profile (CMP)	Toxicology
	Hepatitis C (antibody)		Pregnancy (hcG)
	HIV		

Table 3. Laboratory Assessments. Positive results for reportable communicable diseases will be reported to the public health authority as required by state law. The reportable diseases include HIV, Hepatitis B and Hepatitis C. Subjects will be informed about this requirement in the consent form.

7.3 Special Safety Considerations

7.3.1 MRI-related Risk Minimization

Participants will be appropriately screened for metals as will all personnel who enter the room that contains the MRI scanner. This screening will involve a self-reported MRI safety assessment as per local site policy, and assessment with a ferromagnetic metal detector. All females will have a pregnancy test prior to each MRI scan to ensure that they are not pregnant before being scanned. The following are common sources of risk:

MR sounds.

The MR scanner produces tapping sounds during operation, which may reach very loud levels. To minimize any discomfort from this noise, the participant will be provided with disposable earplugs that suppress external noise levels but do not eliminate voice communication with the scanner operator. The participant will have earplugs, which allow for blockage of environmental noise while maintaining communication and audibility of stimuli. If the participant finds the noise from the scanner objectionable, he/she may stop the study at any time.

Claustrophobia. Some people feel claustrophobic in the MR scanner. If this happens the scan would be stopped immediately. Simulation with the mock scanner will be offered prior to actual scanning to familiarize participants, and minimize this risk.

Neurostimulation. In some cases it is possible that subjects might experience neurostimulation effects, such as muscle twitches and tingling sensations, due to the rapid switching of magnetic field gradients used in these examinations. There are no known risks associated with these effects. Stimulation of the muscles of the heart, causing an abnormal heart rhythm is much less likely to occur. The devices used in this research create magnetic field gradients within the limits specified by the FDA.

Change in Body Temperature. A slight increase in body temperature may occur in the presence of radio frequency waves. A significant, deleterious increase in temperature is very unlikely at the settings employed in this study, which are within FDA guidelines.

RF Antenna Effects. If metal wires or electrodes are attached to a person being imaged, radio frequency signals from the MR scanner may induce sufficient electrical currents in the wires to cause burns where the wires or electrodes contact the skin. If wires or electrodes are present, the scanner operator will inspect and arrange them to minimize the risk of induced currents.

Quench Hazard. The MR scanner uses liquid nitrogen and liquid helium. It is remotely possible that the liquid nitrogen and helium could boil off rapidly and fill the magnet room with extremely cold dense gaseous nitrogen and helium, which can be dangerous if breathed for more than a few moments. When the scanner operator notices a quench, immediate assistance will be provided to anyone inside the magnet room.

Pregnancy. Although there is no known risk to a pregnant woman or her fetus from a MRI scan, women of child-bearing age will be asked to take a urine pregnancy test. If they decline to take the test, they will not be eligible for participation. If the test is positive, they will not be able to participate. There were no adverse effects on embryo-fetal viability, intrauterine growth, or morphological development seen in pivotal reproductive toxicity studies conducted in rats and rabbits (see

Investigator's Brochure). Those who become pregnant during the study will be excluded, and will have appropriate medical care and follow-up arranged.

7.3.2 Data Protection

All subject information will be kept confidential, and only members of the investigative team with appropriate Protection of Human Subjects and HIPAA training will have access to the data. Data will be maintained and secured in locked file cabinets or password-protected electronic media stored on devices approved and maintained for this purpose by Yale University (data coordinating site) in compliance with relevant regulations. Each site will keep a copy of the neuroimaging, behavioral and physiological data at their site. At all sites, digital media and filing cabinets are located in locked offices. A numbering code will be used to assign a unique identifier to each subject. The identification key will be digitally stored separately from all other data, using an encrypted, password protected database. All of the information obtained from subjects is referred to by code number, and kept locked in confidential files. This information is only available to study investigators and to relevant regulatory authorities upon request. As per agreement with the National Institute of Mental Health (NIMH), de-identified data will be shared publicly on the NIMH Data Archive (NDA https://nda.nih.gov/).

7.3.3 Vulnerable subjects

Schizophrenia is a debilitating and burdensome psychiatric illness with prominent cognitive deficits, and no targeted treatments for cognitive deficits. This clinical trial would be a first towards understanding specific neural mechanisms that can be targeted to improve cognition in patients with schizophrenia.

7.3.4 Phlebotomy and IV placement

Bruising, infection and thrombosis can occur with placement of the intravenous line. Having these procedures performed by experienced personnel using good clinical technique minimizes these risks. An experienced physician or nursing staff, as done in our previously completed studies, will perform this aspect of the protocol. Blood volume collection: The total amount of blood donated as part of this study is approximately 70 ml based on approximately 27 ml obtained for baseline laboratory tests, and approximately 40 ml (4 ml per blood levels sample, two samples per test visits, and 5 test visits). For the optional blood draw for genetics, an additional approximately 20 ml of blood will be drawn.

For those patients receiving IV placement, normal saline will be infused at 20 mL/hour. This is considered a slow infusion rate and will be done in order to keep the IV open and avoid clotting.

7.3.5 Blood sampling for pharmacokinetics, preparation, and storage

All efforts will be made to obtain the pharmacokinetic samples at the exact nominal time relative to dosing. However, pharmacokinetics samples obtained within approximately 15% of the nominal time (e.g., within 9 minutes of a 60 minute sample) from dosing will not be captured as a protocol deviation, as long as the exact time of the sample collection is noted on the source document. Sites will be provided materials and training for collecting these samples. Following collection, all samples will be spun, aliquoted and stored at each site, and then sent in batch to a collaborating site, Columbia University, for further storage at -80° Celsius. All processing of samples will be done at Columbia University by the Irving Institute for Clinical and Translational Research. To protect subjects' confidentiality, the banked biospecimens and data generated from them will be coded with the subject's study ID number. Samples will be kept in a locked, limited-access facility. Data will be stored on password-protected computer systems. The key between the code and the subject's personal identifiers will be held at the study site; the researchers using the biospecimens and data generated from them will not have access to the key nor any personally identifying information. Biospecimens will only be used for the purposes described here and in the informed consent document/patient information sheet. Subjects can withdraw their consent for the use of their biospecimens at any time by making a request to the investigator, in which event any remaining biospecimen will be destroyed; data already generated from the biospecimens will continue to be stored to protect the integrity of existing analyses. Results will not be provided to family members or other physicians; nor will they be recorded in the subject's medical record.

7.3.6 Minimizing risk associated with genetic testing.

Genetic samples will be identified with a code number; a password-protected computer file will link subject information to this code. Materials for collecting genetic samples will be provided to each site, and the collected samples will be sent to Yale University for storage. Samples will be stored in a locked -80° C freezer. Any samples shared with other investigators as part of future research protocols utilizing this repository will be identified only by code number; no personal identifying information will ever accompany these samples. Any extracted genetic data will then be made available through the National Institutes of Health database of Genotypes and Phenotypes (daGaP).

7.3.7 Minimizing risk associated with confidentiality.

Patient's charts and written research records will be stored in a locked file cabinet in a secure office, accessible only to the principal investigator and other study personnel. Electronic records of clinical and research data will be stored on a password-protected personal computer. Participants will complete electronic questionnaires in the lab that are on REDCap, which is HIPAA compliant. REDCap is password protected, and will enable de-identified completion of all online questionnaires. We have obtained a Certificate of Confidentiality from the National Institutes of Health to provide maximum protection for the confidentiality of

subjects' clinical and research data.

7.3.8 Minimizing risks associated with neuropsychiatric testing and evaluation.

Some of the questions in the psychiatric interviews may be uncomfortable for the subject to answer. Potential participants may refuse to answer any specific questions or discontinue the interview at any time. The tasks and structured interviews may be tiring, but every effort will be made to avoid making subjects tired. Breaks will be offered frequently and subjects can quit at any time. During the evaluation, unanticipated psychiatric and medical information may be uncovered. In that case, findings will be discussed with the subject and appropriate follow-up will be advised.

7.3.9 Benefits to the participant.

As detailed in the consent form, there may be some benefit as a result of study participation, but no guarantee that individual benefit will be gained from participation in this study.

7.3.10 Alternatives to participation.

Participants are welcome to withdraw at any time, and to refuse participation in the study. The only alternative is to not participate in this study. Refusal to participate will involve no penalty or loss of benefits to which the subject is otherwise entitled.

8. SCHEDULE OF ASSESSMENTS

	\1: ·. 4	\ I : :4 0	\ t ': '4 0	\ \ \ \ \ \ \ \ \ \ \ \ \ \ \ \ \ \ \	\/: · · · =	\ I ' '' \	\/: ·: -
	Visit 1	Visit 2	Visit 3	Visit 4	Visit 5	Visit 6	Visit 7
Visit Windows		Up to 8 weeks from last visit	Between 48 hours-2 weeks of last visit	Between 48 hours-2 weeks of last visit	Between 48 hours-2 weeks of last visit	Between 48 hours-2 weeks of last visit	Up to 1 week from last visit
Informed Consent	Х						
Baseline bloodwork (CBC, CMP, Hepatitis B and C, HIV, optional genetics) EKG, health history, physical exam SCID-V	X						
Fagerstrom Test for Nicotine Dependence	Х						
Calgary Depression Scale for	X						

Schizophrenia							
Beck Anxiety Inventory	Х						
Columbia-Suicide Severity Rating Scale, baseline	Х						
PRA	Х						
Edinburgh Handedness Inventory	X						
Penn CNB n-back letter task only	Х						
Spatial Working Memory task (training)	X						
Flashing Checkerboard task (practice)	Х						
Randomization for dose of CVL-562	X						
Mock scanner experience (optional)	Х						
COVID-19 testing	X	(X)	(X)	(X)	(X)	(X)	(X)
MRI Safety	Х	Х	Х	Х	Х	Х	
Assessment							
Urine toxicology	X	X	X	X	X	X	
Urine pregnancy test	X	X	X	X	X	X	X
Vital Signs	X X	X	X	X	X	X	
Concomitant Medications	X	X	X	X	X	X	
PANNS, pre-dose	X	X	X	X	X	X	
Spatial Working memory task and Flashing Checkerboard Task (refresher)		X	X	X	X	X	
Dose of CVL-562		Х	Х	Х	Х	Х	
Lifestyle Questionnaire, pre -dose		X	X	X	X	X	
Neuroimaging session, including structural MRIs, Spatial Working Memory TaskfMRI,		Х	Х	Х	Х	Х	

resting-state fMRI, ASL, flashing checkerboard stimuli, and DWI (for first visit only), post-dose							
Blood draw for CVL- 562 levels, post-dose (pre-scan and post- scan)		X	X	X	X	X	
Columbia-Suicide Severity Rating Scale, since last visit; pre-dose and post- dose		Х	Х	Х	Х	Х	
PANNS, post-dose		Х	Х	Х	Х	Х	
PennCNB battery, post-dose		Х	Х	Х	Х	Х	
Adverse events	Χ	X	X	X	X	X	X
Follow-up/Debriefing							Х
Final labwork (CBC, CMP)							Х

Table 4. Schedule of Assessments. Visit 2 will occur 8 weeks after consent. All participants will be called approximately 24 hours after each treatment visit (Visits 2-6) to assess for adverse effects. All participants will be called 1 month after the final visit (Visit 7) to assess for lingering adverse effects. For those participants that need to be re-screened, all screening measures will be repeated except the SCID-V, the PRA and the Edinburgh Handedness Inventory.

9. ASSESSING AND REPORTING ADVERSE EVENTS

9.1 Definition

Adverse Event. An adverse event (AE) is defined as any untoward medical occurrence in a study participant taking the study drug(s) which does not necessarily have a causal relationship with the study drug(s). An adverse event can be any unfavorable and unintended sign (including an abnormal laboratory finding), symptom, or disease temporally associated with the use of the study drug(s) or protocol-specified procedure, whether or not considered related to the study drug(s) or protocol-specified procedure. Any worsening (i.e., any clinically significant adverse change in frequency and/or severity) of a pre-existing condition that is temporally associated with the use of the study drug(s), is also an adverse event.

Serious adverse event. A serious adverse event (SAE) is an AE that fulfills one or more of the following criteria:

- 1. Results in death
- 2. Is immediately life-threatening
- 3. Requires in-patient hospitalization or prolongation of existing hospitalization

- 4. Results in persistent or significant disability or incapacity
- 5. Results in a congenital abnormality or birth defect
- 6. Is an important medical event that may jeopardize the subject or may require medical intervention to prevent one of the outcomes listed above

9.2 Evaluating Adverse Events Including Serious Adverse Events

AE Severity

An investigator who is a qualified physician will evaluate all adverse events for severity according to the following criteria:

- Mild (Grade 1) corresponds to an event not resulting in disability or incapacity and which resolves without intervention
- Moderate (Grade 2) corresponds to an event not resulting in disability or incapacity but which requires intervention
- Severe (Grade 3) corresponds to an event resulting in temporary disability or incapacity and which requires intervention
- Life-threatening (Grade 4) corresponds to an event in which the study participant was at risk of death at the time of the event
- Fatal (Grade 5) corresponds to an event that results in the death of the study participant

AE Expectedness

An investigator who is a qualified physician will evaluate AEs for expectedness. AEs can be 'Unexpected' or 'Expected'. Most common Expected AEs include headaches, nausea, fatigue and vomiting. Please refer to the investigative brochure (IB) for additional information.

Unexpected AEs are those AEs in which the nature, severity, or frequency is not consistent with either:

- 1) The known or foreseeable risk of AEs associated with the procedures involved in the research that are described in (a) the protocol-related document, such as the IRB-approved research protocol, any applicable investigator's brochure, and the current IRB-approved informed consent document, or (b) other relevant sources of information, such as product labeling and package inserts; or
- 2) The expected natural progression of any underlying disease, disorder, or condition of the study participant(s) experiencing the AE and the study participant's predisposing risk factor profile for the AE.

AE Attribution

An investigator who is a qualified physician will evaluate AEs for attribution. The investigator must attempt to determine if an AE is in some way related to the use

of the study drug and define an attribution category. This relationship should be described as follows:

Definite – The AE is clearly related to the study drug. The event follows a reasonable temporal sequence from administration of the study drug, the event follows a known response pattern to the study drug and based on the known pharmacology of the study drug, the event is clearly related to the effect of the study drug. The AE improves upon discontinuation of the study drug and reappears upon repeat exposure.

- Probable The AE is likely related to the study drug. The event follows a reasonable temporal sequence from administration of the study drug, the event follows a known response pattern to the study drug AND the event cannot have been reasonably explained by an intercurrent medical condition OR the event cannot be the effect of a concomitant medication.
- Possible The AE may be related to the study drug. The event follows a reasonable temporal sequence from administration of the study drug and the event follows a known response pattern to the study drug BUT the event could have been produced by an intercurrent medical condition which, based on the pathophysiology of the condition, and the pharmacology of the study drug, would be unlikely related to the use of the study drug OR the event could be the effect of a concomitant medication.
- · Unlikely The AE is doubtfully related to the study drug. AE does not have temporal relationship to intervention, could readily have been produced by the study participant's clinical state, could have been due to environmental or other interventions, does not follow known pattern of response to intervention, does not reappear or worsen with reintroduction of intervention.
- · Unrelated The AE is clearly NOT related to the study drug. The event is clearly due to causes distinct from the use of the study drug, such as a documented preexisting condition, the effect of a concomitant medication, or a new condition, which, based on the pathophysiology of the condition, and the pharmacology of the study drug, would be unrelated to the use of the study.

All SAEs will be reported to the project manager within 24 hours of the site becoming aware of the event.

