9.3 Procedures

- AEs will be recorded from the time the consent form is signed through 30 days after the last visit (i.e., at the one month follow-up from Visit 7).
 In addition, SAEs will be reported to the appropriate regulatory authorities, the IRB of Record, and investigators in accordance with all applicable laws and regulations.
- AE reporting must also be carried out by each participating site investigator, according to their local policies and procedures, to the IRB responsible for oversight of their subjects. A copy of the IRB's acknowledgement will be forwarded to the study project manager. In addition, all AEs will be recorded on an Adverse Event Log at each site and entered in REDCap within 72 hours of the site staff becoming aware of the event. All AEs must be followed until resolution or stabilization.
- Unanticipated and unexpected problems involving risk to the subject and/or others, whether related or unrelated to participation in the study, must be reported within 24 hours of the site staff becoming aware of the event to the study project manager. The project manager shall report all SAEs to the Sponsor Principal Investigator, who shall review and evaluate the evidence, and collaborate with the site PI on the final determination regarding attribution for reporting purposes to the following: FDA, Data Safety Monitoring Board (DSMB), Advarra, and/ or Cerevel.
- SAEs which occur any time after the study participant has consented until one month (defined as 30 days) after Visit 7 (i.e., at the final followup phone call) which are unexpected and possibly, probably, or definitely related to the research must be reported by the participating site to the study project manager within 24 hours of the site staff becoming aware of the event.
- FDA and Cerevel Reporting
- The Sponsor Principal Investigator's Investigational New Drug (IND) office will report SAEs to the FDA (if required) via an IND Safety Report on 3500A MedWatch form according to FDA 21CFR312.32 within 15 calendar days of the event occurring (within 7 days if the event is fatal or life-threatening). The Sponsor Principal Investigator's project manager will also report to Cerevel within that same time period.
- Advarra Reporting

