- Each site investigator and/or designee will promptly report unanticipated problems occurring at the site to Advarra as per their written policies and procedures. SAEs that do not require prompt reporting will be reported at the time of continuing IRB review per their written policies and procedures via the Advarra CIRBI platform.

- Reporting to DSMB and NIMH
- Any actions taken by one entity in response to adverse event reports will be reported to the other entities. SAEs that are unexpected, and possibly, probably, or definitely related to the intervention will be reported to the DSMB by the study project manager in writing within 24 hours of awareness of the event. All other SAEs, expected or nonserious adverse events, will be reported to the DSMB in the DSMB data reports submitted every 6 months or at the time of continuing IRB review of the study, and to the FDA in the IND annual report. DSMB recommendations/outcomes will be made available to the NIMH.
- COVID-19-related AEs and SAEs
- All AEs and SAEs that are confirmed, or suspected to be related to, COVID-19 will be tracked within the REDCap system. These AEs and SAEs will be evaluated and reported using the same criteria as other AEs and SAEs.

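### The attribution criteria in 9.2 keep an SAE with no known response pattern below Possible, so it misses the 24-hour written DSMB report

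*Combined protocol and SAP*

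**What the plan says.** Section 9.2 of the protocol has a physician investigator rate each AE separately for expectedness and for attribution.

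- **Unexpected:** "Unexpected AEs are those AEs in which the nature, severity, or frequency is not consistent with either" the risks described in the study documents or the expected course of the participant's own condition.
- **Definite:** plausible timing, and "the event follows a known response pattern to the study drug and based on the known pharmacology of the study drug" a clear relation, with improvement on stopping and recurrence on re-exposure.
- **Probable:** plausible timing, with this requirement: "the event follows a known response pattern to the study drug AND the event cannot have been reasonably explained by an intercurrent medical condition"; alternatively, a concomitant medication cannot be the cause.
- **Possible:** plausible timing, with this requirement: "the event follows a known response pattern to the study drug BUT the event could have been produced by an intercurrent medical condition"; alternatively, a concomitant medication could be the cause.
- **Unlikely:** a list of features that includes "does not follow known pattern of response to intervention". The list also covers lack of a temporal link, other plausible causes, and no return on re-exposure. The text does not say whether one feature is enough or all are needed.
- **Unrelated:** "The event is clearly due to causes distinct from the use of the study drug".

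Section 9.3 then uses both ratings together: "SAEs that are unexpected, and possibly, probably, or definitely related to the intervention will be reported to the DSMB" in writing within 24 hours. Every other SAE goes to the DSMB in the 6-monthly data reports or at continuing IRB review. For the sites, Section 9.3 limits one 24-hour duty to SAEs "which are unexpected and possibly, probably, or definitely related to the research must be reported by the participating site to the study project manager", while Section 9.2 closes by sending every SAE to the project manager on the same clock.

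**The concern.** Expedited reporting to a DSMB exists largely to surface harms that nobody has seen before. Here, the feature that makes an event new also bars it from the relatedness rating that starts the 24-hour clock. A first-ever serious reaction soon after dosing, with no competing explanation, is the case a DSMB would most want to see early, and it is the case the written criteria handle worst.

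The base for judging a known pattern is small. The prior studies in Table 1 (Section 4.5) total 39 + 40 + 13 + 5 + 12 + 77 + 103 = 289 participants, of whom 103 had schizophrenia. Several of those studies were placebo-controlled, and the table does not say how many participants received only placebo. The trial itself plans up to 120 patients with four active single doses each, at most 120 × 4 = 480 active doses, so a reaction not seen before is a realistic possibility.

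**Working it through.** The plan gives no figure to reproduce. The check is a logical one: code the five definitions, remove the known pattern, and see which ratings remain open.

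**Inputs (all from Section 9.2).** T = plausible timing; K = known response pattern; I = an intercurrent condition could explain the event; C = a concomitant medication could explain it; R = positive re-exposure; X = clearly another cause.

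**Rules on the natural reading**, where the final OR joins only the two alternative explanations:

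- Definite = T and K and R
- Probable = T and K and (not I or not C)
- Possible = T and K and (I or C)
- Unlikely = features drawn from: not T; I or X; C or X; not K; not R
- Unrelated = X

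**Step 1. Remove the known pattern.** With K = no, five yes/no features remain, giving 2^5 = 32 combinations. K is a required term in Definite, Probable and Possible, so 0 of 32 reach any of them and 0 of 32 trigger the 24-hour DSMB report.

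**Step 2. Where these events land.**

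- If any one Unlikely feature is enough, lack of a known pattern alone places all 32 in Unlikely (those with X also meet Unrelated).
- If all the features are needed, the 16 combinations with X = yes are Unrelated. Of the 16 with X = no, only one (not T, I, C, not R) is Unlikely. The other 16 − 1 = 15 fit no category, and 8 of these have plausible timing. With plausible timing and no alternative cause (I = C = no), 2 combinations remain, and neither has a category.

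**Step 3. The other reading of OR.** If each OR opened a stand-alone criterion, Probable would follow from not C and Possible from C, so 32 of 32 would qualify. But any event not attributable to a concomitant medication would then be Probable whatever its timing, which cannot be meant.

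**Step 4. Contrast.** With T and K both yes, either Probable or Possible is always met. An SAE of known pattern that is unexpected in severity or frequency therefore still triggers the report. The gap is specific to events without a known pattern.

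**Step 5. Routes and clocks side by side.**

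| Route | Section | Relatedness needed | Clock | DSMB reached |
|---|---|---|---|---|
| Written SAE report | 9.3 | Possible or higher, and unexpected | 24 hours | Yes |
| Data report for all other SAEs | 9.3 | No | 6-monthly or at continuing IRB review | Yes |
| All SAEs to project manager | 9.2 | No | 24 hours | No |
| Unanticipated problems to project manager | 9.3 | No | 24 hours | No |
| Sponsor PI review and final attribution | 9.3 | Decided here; no separate criteria | None stated | Only through the resulting report |
| Reportable Events | 11.2.2 | Possible or higher | Immediately if possible; written in 5 calendar days | Not named |
| Unanticipated problems that may interrupt the study | 11.2.2 | None stated | As above | Not named |
| Unanticipated SAEs to monitors, sponsors, agencies and decision-making bodies | 11.2.2 | None stated | 5 days | Not named |
| DSMB review of SAEs | 11.2.3 | None stated | 7 days | Yes; delivery route not given |

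**The case against.** The strongest reply is that the gap affects one notice among several. Every SAE reaches the project manager within 24 hours and then the sponsor PI, who settles attribution with the site PI, so the site rating is not final. Unanticipated problems go to the project manager on the same clock whether or not they are related. Section 11.2.2 adds a 5-day notice of unanticipated SAEs with no relatedness condition. Section 11.2.3 has the DSMB review SAEs within 7 days, again with no such condition. The sponsor PI, IRB, FDA and NIMH can each stop or suspend the study. All of this stands and limits the consequence. It does not restore the 24-hour DSMB report: the sponsor PI has no other category definitions to apply, and the 5-day notice does not name the DSMB.

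A second reply is that known response pattern is undefined, and that expectedness is judged against listed documents. An event missing from those documents could still be thought to fit the drug's pharmacology. That also stands: unexpected in nature and lacking a known pattern overlap, but the protocol does not equate them. The point therefore concerns SAEs with no known pattern, not every SAE unexpected in nature.

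A third reply is that an investigator could rely on the opening line of Possible, which speaks only of an event that may be related. In practice some would, but only by setting aside the conditions that follow it.

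**Conclusion.** The point holds for one route. On the written criteria, an SAE with no known response pattern cannot be rated Possible or higher (0 of 32 combinations), so it does not trigger the 24-hour written DSMB report. For such an event, DSMB timing moves from 24 hours to 7 days if Section 11.2.3 governs, or to as long as about 6 months if the default in Section 9.3 governs. The protocol does not say which prevails.

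A reader might infer two stronger things that the documents do not support. One is that such an event can only be rated Unlikely or Unrelated: if the Unlikely features are cumulative, a well-timed event with no other cause fits no category at all. The other is that the DSMB would simply not hear for six months while nobody able to act has been told: Sections 9.2, 9.3, 11.2.2 and 11.2.3 contain routes at 24 hours, 5 days and 7 days that do not depend on attribution.

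The conclusion rests on the natural reading of the OR clauses and on taking the listed conditions as requirements, as their wording indicates. It is a drafting defect with a safety consequence, worth correcting at the next amendment. Because of the other routes, it does not rank among the most serious problems a plan can have.

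**What to change.** In Section 9.2:

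- Make fit to a known response pattern supporting evidence, not a required condition, for Possible and Probable.
- Let Possible cover plausible timing where a causal role cannot be ruled out, with or without an alternative cause.
- State that lack of a known pattern does not by itself make an event Unlikely.

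In the same amendment, reconcile the SAE routes and clocks:

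- Align the site duty in 9.3 with the all-SAE rule that closes 9.2.
- Settle whether SAEs outside the 24-hour report reach the DSMB within 7 days (11.2.3) or in the 6-monthly report (9.3), and name the delivery route.
- Say whether the decision-making bodies in the 5-day notice of 11.2.2 include the DSMB.

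The cost is protocol wording, site retraining and a few more events rated Possible and sent as expedited reports. The endpoints, sample size and analyses are unaffected.
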